4.3 Criteria for Subsequent Therapy

All patients must meet the minimal criteria for subsequent therapy: the absolute neutrophil count $\geq 1,000 / \mu\text{L}$, the platelet count $\geq 50,000 / \mu\text{L}$, and the resolution of toxicity to $\leq \text{Grade 1}$, pre-therapy baseline, or Grade 2 that is not clinically significant. Toxicities are graded by using NCI CTCAE v5.0 toxicity criteria.

In general, treatment should be on hold if the minimal criteria for subsequent therapy are not met. However, the patient may resume therapy if and when the physician and the patient believe that further treatment will benefit the patient. Supportive care will be allowed according to good clinical practice.

Remote Procedures

In case of any unexpected incidents that patients can't come back to MD Anderson Cancer Center for study treatment and assessments, remote procedures can be applied for this trial conduction, including remote consent, remote toxicity assessment via phone calls, virtual visit, etc., with compliance with institutional policies. Patients can have lab work, scheduled scans, physical exams and receive treatment locally if applicable. Laboratory work done at an outside facility is to be forwarded to the subject's attending physician at MD Anderson or the PI of the study, who will date and sign off on the labs to verify the results were reviewed. Remote monitoring can be applied as needed. Study drug may be mailed to the patient per institutional guidelines/approval.

4.4 Dose Delays and Modifications

In addition to the following general guidelines for dose delays and modifications, the treating physicians as well as the study chair may institute additional remedies in the best interests of their patients according to their best medical knowledge.

The patients may interrupt treatment during study for palliative radiation or surgery, and may resume therapy when they recover, according to good medical practice.

If a patient experiences a clinically relevant toxicity which is known to be related to one drug in the regimen, then that drug may be modified according to the recommendation for that drug. Patient continuation on one single agent is allowed.

If a patient experiences a clinically relevant toxicity for which it is unclear which drug is the cause of the toxicity, then both agents may be modified according to the recommendation for each agent.

After a dose reduction for any toxicity, re-escalation is not permitted. For Grade 4 or recurrent G3 eye-related toxicities, the investigational treatment must be permanently discontinued.

Dose Delays and Modification Specific for Futibatinib

Description of Futibatinib – please see investigator's brochure (IB).

Futibatinib is a novel and selective small molecule irreversible, covalent inhibitor of fibroblast growth factor receptor (*FGFR*) 1–4.

Futibatinib will be supplied by Taiho Oncology, Inc. (Taiho). Detailed information, such as the requirements for accountability and disposal of study drug, can be found in the Pharmacy Manual, which will be provided separately.

Description of Study Drug

Futibatinib will be provided as 4-mg tablets for oral use. Please refer to the Investigator's Brochure for additional information.

Packaging and Labelling

Futibatinib will be packaged and labelled according to local laws and regulations.

Handling and Storage

Futibatinib tablets should be stored in accordance with the label.

Treatment Administration

Futibatinib is supplied as 4 mg tablets and will be taken orally at a dose of 20 mg daily until the patient meets any of the administration discontinuation or dose reduction criteria.

Futibatinib should be administered without or with food, with a glass of water.

In the event of a dosing delay up to 12 hours after the scheduled dosing time, the patient should still take that day's dose. If the dosing delay continues for >12 hours after the scheduled dosing time, or if the patient vomits after a dose, the patient should skip dosing for that day and not make up for it the following day.

Recommended Dose Modifications for Futibatinib

Stepwise dose reductions of 4 mg to 16 mg (first reduction) and 12 mg (second reduction) are permitted based on toxicities. If dose reduction fails to result in achieving the minimal criteria to resume treatment or, if toxicities occur which would necessitate reduction of the dose of futibatinib below 12 mg QD, the patient should be discontinued from futibatinib.

Following a dose reduction, if a benefit/risk assessment favors an increase of futibatinib dose up to the initial starting dose an agreement with the Sponsor's medical monitor is required prior to the dose increase.

If toxicities do not recover based on the criteria defined below within 28 days after the last dose of futibatinib, the patient will be discontinued permanently from treatment. If resumption criteria are met within 28 days of the last dose of futibatinib, the patient may resume futibatinib treatment at the appropriate dose level.

Dose Modifications for Nonhematologic Toxicities

Dosing modification guidelines for nonhematologic and eye toxicities are provided in **Table 4**

Please see futibatinib package insert for details.

(https://www.accessdata.fda.gov/drugsatfda_docs/label/2022/214801Orig1s000lbl.pdf)

Table 4: Recommended Dose Modifications for Related Nonhematologic Toxicities

Adverse Reaction	Severity	Futibatinib Dosage Modifications
Retinal Pigment Epithelial Detachment (RPED)	Not applicable	
Continue at the current dose and continue periodic ophthalmic evaluation:
 
 • If resolving within 14 days, continue at the current dose. • If not resolving within 14 days, withhold until resolving; then resume at previous or a lower dose
Hyperphosphatemia	
Serum phosphate $\geq 5.5 - \leq 7$ mg/dL
 
Serum phosphate $> 7 - \leq 10$ mg/dL
 
Serum phosphate >10 mg/dL
	
Continue at the current dose and initiate phosphate lowering therapy. Monitor serum phosphate weekly.
 
• Initiate or adjust phosphate lowering therapy. Monitor serum phosphate weekly and Dose reduced to next lower dose
 
 - If the serum phosphate resolves to ≤ 7 mg/dL within 2 weeks after dose reduction, continue at this reduced dose. - If serum phosphate is not ≤ 7 mg/dL within 2 weeks, further reduce to the next lower dose. - If serum phosphate is not ≤ 7 mg/dL within 2 weeks after the second dose reduction, withhold until serum phosphate is ≤ 7 mg/dL and resume at the dose prior to suspending. 
Initiate or adjust phosphate lowering therapy and monitor serum phosphate weekly and
 
 • Withhold until phosphate is ≤ 7 mg/dL and resume at the next lower dose. - Permanently discontinue if serum phosphate is not < 7 mg/dL within 2

		weeks following 2 dose interruptions and reductions.
Other Adverse Reactions	Grade 3 ^a	Withhold until toxicity resolves to Grade 1 or baseline, then resume - for hematological toxicities resolving within 1 week, at the dose prior to suspending. - for other adverse reactions, at next lower dose.
	Grade 4 ^a	Permanently discontinue

^a Severity as defined by National Cancer Institute Common Terminology Criteria for Adverse Events (NCI CTCAE version 5.0).

Dose Modifications for Hematologic Toxicities are presented in [Table 5](#).

Table 5: Futibatinib Dose Interruption and Modification for Related Hematologic Toxicities

CTCAE Grade (value)	Recommended dose modification any time during a cycle of futibatinib ^a
Anemia (Hgb)	
Grade 1 (Hgb < LLN - 10.0 g/dL)	Maintain dose level
Grade 2 (Hgb < 10 – 8.0 g/dL)	Maintain dose level
Grade 3 (Hgb < 8.0 - 6.5 g/dL)	Withhold dose until resolved to ≤ Grade 1 or baseline, • If resolved ≤7 days, then maintain dose level • If resolved >7 days, then reduce 1 dose level
Grade 4 (life threatening consequences; urgent intervention indicated)	Withhold dose until resolved to ≤ Grade 1 or baseline, then reduce 1 dose level
Neutropenia (ANC)	
Grade 1 (ANC < LLN - 1500/mm ³)	Maintain dose level
Grade 2 (ANC < 1500 - 1000/mm ³)	Maintain dose level
Grade 3 (ANC < 1000 - 500/mm ³)	Maintain dose level
Grade 4 (ANC < 500/mm ³)	Withhold dose until resolved to ≤ Grade 2 or baseline, • If resolved ≤7 days, then maintain dose level • If resolved >7 days, then reduce 1 dose level
Febrile neutropenia: ANC < 1000/mm ³ , and with a single temperature > 38.3°C (101°F) or a sustained temperature ≥ 38°C (100.4°F) for more than one hour.	Withhold dose until resolved, then reduce 1 dose level
Thrombocytopenia	
Grade 1 (PLT < LLN - 75,000/mm ³)	Maintain dose level
Grade 2 (PLT < 75,000 - 50,000/mm ³)	Maintain dose level
Grade 3 (PLT < 50,000 - 25,000/mm ³)	Withhold dose until resolved to ≤ Grade 1 or baseline, • If resolved ≤7 days, then maintain dose level • If resolved >7 days, then reduce 1 dose level
Grade 4 (PLT < 25,000/mm ³)	Withhold dose until resolved to ≤ Grade 1 or baseline, then reduce 1 dose level

Abbreviations: ANC=absolute neutrophil count; CTCAE=Common Terminology Criteria for Adverse Events; Hgb=hemoglobin; LLN=lower limit of normal; PLT=platelets.

a. Interrupt futibatinib if any toxicities are intolerable, regardless of the grade (including Grade 1 and 2). If or when the toxicity resolves to a tolerable state, consideration can be given to resuming futibatinib at the same dose if deemed appropriate or reduced by one dose level if needed.

Dose Modifications in Case of Induced Drug Liver Injury (Hy's Law)

Futibatinib will be permanently discontinued (pembrolizumab is allowed to be administered as a single agent if there is no tumor progression and no pembrolizumab related prohibitive toxicity) if liver function test abnormalities fulfill Hy's Law criteria defined as concurrent observation of the following, with no other reason found to explain the findings (such as viral hepatitis A, B, or C; preexisting or acute liver disease; liver metastases; or another drug capable of causing the observed liver injury):

- Elevated aminotransferase enzymes of $>3 \times$ ULN (upper limit of normal)
- Alkaline phosphatase (ALP) $<2 \times$ ULN
- Associated with an increase in bilirubin $\geq 2 \times$ ULN

Dose Delays and Interruptions Specific for Pembrolizumab

Description of Pembrolizumab: please see pembrolizumab packaging insert.

Pembrolizumab is a potent humanized immunoglobulin G4 (IgG4) monoclonal antibody (mAb) with high specificity of binding to the programmed cell death 1 (PD-1) receptor, thus inhibiting its interaction with programmed cell death ligand 1 (PD-L1) and programmed cell death ligand 2 (PD-L2). Based on preclinical in vitro data, pembrolizumab has high affinity and potent receptor blocking activity for PD-1. Pembrolizumab has an acceptable preclinical safety profile and is in clinical development as an intravenous (IV) immunotherapy for advanced malignancies. Keytruda® (pembrolizumab) is indicated for the treatment of patients across a number of indications.

Pembrolizumab will be obtained commercially and its cost will be covered by patients and/or their insurance companies.

Administration

Intravenous pembrolizumab 200 mg will be administered once every 3 weeks for up to 2 years as long as the patient is receiving benefit, tolerating the regimen, and does not meet any criteria for discontinuation of study treatment.

Recommended Dose Delays and Interruptions for Pembrolizumab

No dose reductions of KEYTRUDA are recommended. Withhold or discontinue KEYTRUDA to manage adverse reactions as described in [Table 6](#). Severity and type of reaction are graded according CTCAE 5.0. Please see Pembrolizumab package insert for details.

Table 6. Pembrolizumab Dose Delays and Interruptions Guidelines

Adverse Reaction	Severity	Dose Delays/Interruptions
Other immune-mediated adverse reaction	Grades 2 or 3 based on the severity and type of reaction	Withhold Resume when the immune-mediated adverse reaction resolves to Grade 1 or 0 following corticosteroid taper
	Grade 3 based on the severity and type of reaction or Grade 4	Permanently discontinue
Recurrent immune-mediated adverse reactions	Recurrent Grade 2 pneumonitis	Permanently discontinue
	Recurrent Grades 3 or 4	
Inability to taper corticosteroid	Requirement for 10 mg/day or greater prednisone or equivalent for more than 12 weeks after last dose of pembrolizumab.	Permanently discontinue
Persistent Grade 2 or 3 (excluding endocrinopathy)	Grades 2 or 3 adverse reactions lasting 12 weeks or longer after last dose of pembrolizumab	Permanently discontinue

Concomitant Medications and Therapies

Prohibitive Medications and Therapies

Patients are not permitted to receive any other investigational or any other anticancer therapy, including chemotherapy, immunotherapy, biological response modifiers, or antineoplastic endocrine therapy during the study treatment period.

Extended-field radiation therapy or palliative radiation to a focal site of measurable disease is also prohibited. If it is deemed in the best interest of the patient and after discussion between the Investigator and Medical Monitor, it can be administered, but the patient will be censored for the primary endpoint analysis.

Immunosuppressive therapy including steroids (> 10 mg/day prednisone or equivalent) is not permitted with pembrolizumab.

Concomitant strong inhibitors and inducers and sensitive substrates of CYP3A4 should be avoided, if possible, with futibatinib. Caution is advised if these drugs are given concomitantly (see [Appendix A: CYP3A4 and Transporters – Classification of Substrates, Inhibitors, and Inducers of CYP Enzymes and Transporters](#)). Alternative replacement is highly recommended.

Concomitant Medications and Therapies Requiring Precautions

Supportive treatment is allowed based on available institutional or local guidelines.

Local or regional palliative cryotherapy or radiation, such as for bone pain or palliative surgery (non-anti-neoplastic intent), are permitted (provided the target lesion is not a site of measurable disease and is not indicative of disease progression). Study therapy should be ceased a minimum of 2 days prior to administration of palliative treatment, and may be resumed 7 days after the procedure or when the patient has recovered from the side effects of the procedure.

The following medications/therapies may be given concomitantly under the following guidelines:

Hematologic Support: may be administered as medically indicated (that is, blood transfusions, granulocyte colony-stimulating factor, erythropoietin stimulating agents) according to the institutional site standards or American Society of Clinical Oncology (ASCO) guidelines ⁷⁶.[76].

Management of Diarrhea: Prophylactic treatment for diarrhea is permitted during the study if clinically indicated according to the institutional or published guidelines ⁷⁷.

Management of Nausea/Vomiting: Antiemetics may be administered as clinically indicated according to institutional standards or ASCO guidelines ⁷⁸.

Drug Interactions

Three clinical drug-drug interaction studies and 1 PK model analysis in humans showed that moderate to strong inhibitors or inducers of CYP3A have potential clinical drug-drug interactions with futibatinib: please see IB and futibatinib package insert for details.

Futibatinib is a substrate of CYP3A and P-gp.

Dual P-gp and Strong CYP3A Inhibitors

- Avoid concomitant use of drugs that are dual P-gp and strong CYP3A inhibitors with futibatinib.
- Concomitant use of drugs that are dual P-gp and strong CYP3A inhibitors with futibatinib may increase futibatinib exposure, which may increase the incidence and severity of adverse reactions.

Dual P-gp and Strong CYP3A Inducers

- Avoid concomitant use of dual P-gp and strong CYP3A inducers with futibatinib.
- Concomitant use of drugs that are dual P-gp and strong CYP3A inducers may decrease futibatinib exposure, which may reduce the efficacy of futibatinib.

Overdose

As of the cut-off date for the Development Update Safety Report (DSUR) for futibatinib (23 January 2020), there were 2 cases of overdose reported in the TAS-120-101 trial. Two patients with cholangiocarcinoma took a higher than planned dose of futibatinib for 1 day. There were no adverse events associated with the overdose.

Effective Contraception During Study

Female patients considered not to be of childbearing potential must have a history of being postmenopausal (no menses for 12 months without an alternative medical cause), or hysterectomy that is clearly documented in the patient's source documents.

For WOCBP, including female study participants and partners of male participants, effective contraception is required during the study and for 180 days after the last dose of study medication, or longer if necessary based on local requirements. Effective contraception is defined as follows:

- Combined (estrogen and progestogen containing) hormonal contraception associated with inhibition of ovulation:
 - Oral – Intravaginal – Transdermal
 - Progestogen-only hormonal contraception associated with inhibition of ovulation:
 - Oral – Injectable – Implantable
- Intrauterine device
- Intrauterine hormone-releasing system
- Bilateral tubal occlusion
- Vasectomized partner with documentation of the success of the vasectomy

- Complete abstinence from heterosexual intercourse (periodic abstinence is not a safe method)

Donation of ova is not allowed during the study and for 180 days or longer based on local requirements following the last dose of study drug.

Definitions of “Women of Childbearing Potential”, “Women of No Childbearing Potential”

As defined in this protocol, “women of childbearing potential” are females who are physiologically capable of becoming pregnant.

Conversely, “women of no childbearing potential” are defined as females meeting any of the following criteria:

- Surgically sterile (i.e., through bilateral salpingectomy, bilateral oophorectomy, or hysterectomy)
- Postmenopausal, defined as:
 - ≥ 55 years of age with no spontaneous menses for ≥ 12 months OR
 - < 55 years of age with no spontaneous menses for ≥ 12 months AND with a postmenopausal follicle-stimulating hormone concentration > 30 IU/mL and all alternative medical causes for the lack of spontaneous menses for ≥ 12 months have been ruled out, such as polycystic ovarian syndrome, hyperprolactinemia, etc.

If an FSH measurement is required to confirm postmenopausal state, concomitant use of hormonal contraception or hormonal replacement therapy should be excluded.

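### Table 4 does not carry Section 4.4's mandatory stop for Grade 4 or recurrent Grade 3 eye toxicity: its ungraded RPED row contradicts the stop at any dose, and its Grade 3 'Other' row does so for recurrent events while a lower dose remains

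*Combined protocol and SAP*

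**What the plan says.** The general part of Section 4.4 sets a mandatory rule: "For Grade 4 or recurrent G3 eye-related toxicities, the investigational treatment must be permanently discontinued". Further on, under dose modifications for nonhematologic toxicities, the section says "Dosing modification guidelines for nonhematologic and eye toxicities are provided in" Table 4.

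The only eye event that Table 4 names is RPED. The severity cell of that row reads 'Not applicable'. The action is "Continue at the current dose and continue periodic ophthalmic evaluation". If the event is resolving within 14 days the dose is unchanged; otherwise the row says "If not resolving within 14 days, withhold until resolving; then resume at previous or a lower dose".

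Any other eye event falls under the 'Other Adverse Reactions' rows. For Grade 3 the instruction is "Withhold until toxicity resolves to Grade 1 or baseline, then resume", and for events that are not hematological the dose on resumption is given as "for other adverse reactions, at next lower dose". For Grade 4 the instruction is permanent discontinuation.

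The dose steps and the floor are in the text before the table: "Stepwise dose reductions of 4 mg to 16 mg (first reduction) and 12 mg (second reduction) are permitted based on toxicities", and "if toxicities occur which would necessitate reduction of the dose of futibatinib below 12 mg QD, the patient should be discontinued from futibatinib".

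**The concern.** Section 4.4 gives two instructions for the same event. The general rule says that the patient must stop for good. The table that the section itself designates for eye toxicities says to carry on, or to pause and restart. An investigator who works from the table could re-dose a patient whom the protocol requires to stop.

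The plan treats severe eye toxicity as important. It has its own stopping rule, Section 6.2 has Grade 3 and 4 eye toxicities reported as SAEs, and Section 5.2 schedules repeated eye examinations with OCT. Section 2.2 also reports Grade 3 or higher ocular toxicity, in a group that includes RPED, in 10% of patients on erdafitinib, another FGFR inhibitor. Severe grades are therefore foreseeable. What is at stake is patient safety and consistent dosing, not the efficacy analysis.

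**Working it through.** No stated figure bears on this point, so the check is a comparison of rules. For each type of eye event, the action under the Section 4.4 stop is set against the action under Table 4 together with the dose floor.

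Inputs, all from Section 4.4:
- The stop applies to Grade 4 and to recurrent Grade 3 eye events. It says nothing about a first Grade 3 event.
- The dose steps are 20 − 4 = 16 mg and 16 − 4 = 12 mg. A further step would be 12 − 4 = 8 mg, which is below the 12 mg floor, so futibatinib stops.
- The 'Other' rows do not reach RPED, which has its own row.

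| Eye event | Section 4.4 stop | Table 4 with the 12 mg floor | Result |
|---|---|---|---|
| RPED, Grade 4, any dose | Stop | Continue, or withhold and resume at the same or a lower dose | Conflict |
| RPED, recurrent Grade 3, any dose | Stop | As above | Conflict |
| RPED, first Grade 3 | No stop | As above | No conflict |
| Other eye event, Grade 4 | Stop | Stop | Agree for futibatinib |
| Other eye event, first Grade 3 | No stop | Next lower dose, or stop at the floor | No conflict |
| Other eye event, recurrent Grade 3 at 16 mg | Stop | Resume at 12 mg | Conflict |
| Other eye event, recurrent Grade 3 at 12 mg | Stop | 8 mg is below 12 mg, so stop | Agree for futibatinib |

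The 12 mg floor does not rescue the RPED row. It acts only when a reduction below 12 mg is needed, and the RPED row allows resumption at the previous dose. That conflict therefore exists at 20, 16 and 12 mg.

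For the 'Other' row, the usual path is a first Grade 3 event at 20 mg with resumption at 16 mg, then a recurrence at 16 mg with resumption at 12 mg, where the stop should already have applied. A recurrence can also meet this row at 20 mg if the first event led to no reduction, for example RPED resumed at the previous dose.

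Two other rules in the plan were checked as possible safeguards:
- Section 4.3 holds treatment until toxicity has settled, but it allows treatment to resume, including at the discretion of physician and patient.
- Section 4.4 permanently stops patients whose toxicity has not recovered within 28 days of the last futibatinib dose. It does not stop a patient whose event resolves in time.

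Neither supplies the stop for a Grade 4 or recurrent Grade 3 event that resolves.

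**The case against.** The strongest reply is that the text can be read as a whole. The eye rule is specific and says 'must', while Table 4 is titled as recommended modifications. On that reading the stop prevails and only a cross-reference is missing. This is the likely intent, but the protocol does not say so. Section 4.4 introduces its rules as general guidelines and then points to the table for eye toxicities in particular, so following the table would also be a reasonable reading.

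A second reply is that the holding rule in Section 4.3 and the 28-day rule limit dosing through a severe event. That stands. A reader might infer from the RPED row that patients would simply be dosed through severe RPED, and the documents do not support that. The gap that remains is re-dosing after the event resolves.

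Three other stronger readings should also be resisted:
- **That the Grade 3 'Other' row conflicts at a first event.** It does not, because the stop covers only recurrent Grade 3 and Grade 4.
- **That the 'Other' row conflict is confined to patients who start at 20 mg, and so can be counted.** The RPED row lets a patient resume at 16 mg after a first event. The futibatinib part of Section 4.4 also allows a dose increase with the medical monitor's agreement, although the general part forbids re-escalation. Either path can put a patient who started at 16 mg in the conflict.
- **That the 10% in Section 2.2 forecasts cases here.** It is a pooled ocular figure for another drug and shows neither Grade 4 nor recurrent Grade 3 RPED. For futibatinib, Section 2.2 describes ocular toxicity as being of low frequency.

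**Conclusion.** The concern holds. Table 4 omits a stop that Section 4.4 makes mandatory. The main conflict is Grade 4 or recurrent Grade 3 RPED, at any futibatinib dose. The narrower one is a recurrent Grade 3 eye event other than RPED while a lower dose remains, typically at 16 mg.

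Few patients, possibly none, would be affected. The documents give no rate for Grade 4 or recurrent Grade 3 eye toxicity, so no count is offered. No endpoint, sample size or error rate changes. It is still worth correcting, because it is a contradiction in a mandatory safety rule and wording alone removes it.

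The conclusion assumes that 'recurrent' means a second Grade 3 eye event, which the protocol does not define, and that the 'Other' rows exclude RPED. Where the two rules agree, they agree for futibatinib only, since Table 4 and the floor govern only that drug. Section 4.2 uses the term 'investigational treatment' for pembrolizumab and futibatinib together, which suggests that the stop covers both. Section 4.4 also allows a patient to continue on one agent, so this should be settled.

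**What to change.** Amend Table 4 in three places:
1. In the RPED row, replace the severity entry with: *below Grade 4 and not recurrent Grade 3*.
2. Add a row: *Grade 4 or recurrent Grade 3 eye-related toxicity (including RPED): permanently discontinue the investigational treatment, per Section 4.4*.
3. In the Grade 3 'Other Adverse Reactions' row, add: *except recurrent Grade 3 eye-related toxicity*.

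The new row should keep the term 'investigational treatment'. Writing futibatinib alone would narrow the stop while citing it. The sponsor should confirm whether both drugs stop and, if only futibatinib is meant, say so in both places.

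The cost is wording: two rows edited and one added, with no new procedure, visit or patient. The only patients whose dosing would change are those whom Section 4.4 already requires to stop.

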4 STUDY DESIGN AND TREATMENT PLAN

4.1 Study Design

This is an investigator-initiated NCCN (National Comprehensive Cancer Network)-supported phase II clinical trial (2020-IST-FUTI-000032) conducted at The University of Texas MD Anderson Cancer Center who will hold the Investigational New Drug (IND) for this study.

After patients with metastatic MSS endometrial carcinoma have signed the informed consent, patients will be enrolled to receive therapy for toxicity and efficacy evaluation.

The dose limiting toxicity (DLT) window is the initial 21 days of therapy.

- Enroll 6 lead-in patients to receive futibatinib 20 mg PO daily plus pembrolizumab 200 mg IV once every 3 weeks on day 1 of each cycle (dose level 1 in Table 1). If there is one or less DLT, the study will continue following a Bayesian optimal phase 2 (BOP2) design at dose level 1.
- If there are two or more DLTs, enroll another 6 lead-in patients to receive futibatinib 16 mg PO daily plus pembrolizumab 200 mg IV once every 3 weeks on day 1 of each cycle (dose level -1 in Table 1).
- If there are two or more DLTs at this dose level, the study will be terminated.
- If there is one or less DLT, the study will continue following a BOP2 design at dose level -1.
- The lead-in patients will be counted as the patients who are enrolled to stage I at the same dose level.

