7 STATISTICAL CONSIDERATIONS

7.1 Study Design

After patients have signed the informed consent, patients will be enrolled to receive therapy for toxicity and efficacy evaluation. One cycle of therapy is 21 days. No randomization is utilized to assign patients in this study.

The DLT window is 21 days after starting the treatment. The trial starts with safety lead-in:

- Six lead-in patients will be enrolled at dose level 1. If there is one or less DLT, the study will continue following a Bayesian optimal phase 2 (BOP2) design.
- If there are two or more DLTs, the study will enroll another six lead-in patients at dose level -1.
- If there are two or more DLTs at dose level -1, the study of that therapy will be terminated.
- If there is one or less DLT, the study will follow a BOP2 design at the dose level -1.
- The lead-in patients are allowed to be counted as the patients enrolled to stage I per a BOP2 design if they initiate the same dose.

The intent-to-treat (ITT) population includes all patients who have received study agents. Efficacy will be analyzed based on the ITT population, following a BOP2 design ^{86,87} with p_0 (historical response rate) = 15% and p_1 (minimum desired experimental response rate) = 40%. The first stage will consist of 12 patients. Accrual will stop at the end of the first stage if fewer than 3 responses are seen. The second stage will consist of 12 patients. We will declare the experimental agent worthy of further study if 7 or more responses are seen in 24 patients. This design has a Type I error rate of 4.9% and an 86% power. The maximum number of patient enrollment is $6 + 24 = 30$, noting that the lead-in patients will be counted as phase II patients.

Below are the operating characteristics of the design using the BOP2 web application, (Table 11), which is available at <http://www.trialdesign.org>.

Table 11: The Operating Characteristics Of The BOP2 Design For This Study

Scenario	Response Rate	Early Stopping (%)	Claim Promising (%)	Average Sample Size
1	0.15	73.58	4.87	15.2
2	0.30	25.28	55.61	21.0
3	0.40	8.34	86.20	23.0
4	0.50	1.93	97.38	23.8

During the phase II part, after 6 patients are treated, at any time > 30% of patients have DLTs, that dose level will be terminated.

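### Section 4.4 states the futibatinib dose and reductions only for a 20 mg start, which conflicts with the dose level -1 cohort that starts at 16 mg and has one reduction available, not two

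*Combined protocol and SAP*

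**What the plan says.** **Starting doses.** Section 4.1 and Table 3 (Section 4.2) define two levels. Level 1: "Enroll 6 lead-in patients to receive futibatinib 20 mg PO daily plus pembrolizumab 200 mg IV once every 3 weeks". If two or more of those six patients have a DLT, the study will "enroll another 6 lead-in patients to receive futibatinib 16 mg PO daily plus pembrolizumab 200 mg IV once every 3 weeks" (level -1). Section 7.1 then says: "If there is one or less DLT, the study will follow a BOP2 design at the dose level -1". Section 7.3 gives a second route: if more than 30% of patients have DLTs during phase II, that level closes and a cohort may open at a lower one.

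**Administration and reductions (Section 4.4).** Futibatinib "will be taken orally at a dose of 20 mg daily until the patient meets any of the administration discontinuation or dose reduction criteria". No exception is made for level -1. The reduction rule reads: "Stepwise dose reductions of 4 mg to 16 mg (first reduction) and 12 mg (second reduction) are permitted based on toxicities". The floor follows: "if toxicities occur which would necessitate reduction of the dose of futibatinib below 12 mg QD, the patient should be discontinued from futibatinib".

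**Phosphate rules (Section 4.4, Table 4).** For phosphate above 7 and up to 10 mg/dL, the dose goes down one step. Next: "If serum phosphate is not ≤ 7 mg/dL within 2 weeks, further reduce to the next lower dose". If the value is still above 7 two weeks after that second reduction, the drug is withheld until it falls and is then resumed at the same dose. For phosphate above 10 mg/dL, permanent discontinuation is tied to two interruptions with reductions.

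**Hematologic rules (Section 4.4, Table 5).** Several rows call for a reduction by one dose level. Table 3 has no level below -1.

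**The concern.** Section 4.4 does not distinguish between the two possible starting doses. For the level -1 cohort, its daily dose contradicts the assigned dose, and the reduction it calls the first is the dose these patients already take. Table 4 depends on two reductions being available, and this cohort has only one.

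Level -1 opens because of toxicity at level 1, so dose-modification rules matter most there. If the rules conflict, patients at the same dose with the same laboratory value can be handled differently. That affects futibatinib exposure and the tolerability data. Safety and tolerability are a primary objective (Section 1.1), and level -1 could carry the whole phase II part.

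**Working it through.** **1. Reduction ladder.** Inputs from Section 4.4: step 4 mg, floor 12 mg. Starting doses from Table 3: 20 mg and 16 mg.

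- 20 mg start: 20 − 4 = 16; 16 − 4 = 12; the next step, 12 − 4 = 8, is below the floor. Two reductions, which reproduces the stated ladder.
- 16 mg start: 16 − 4 = 12; the next step, 8, is below the floor. One reduction. The named first reduction, to 16 mg, gives 16 − 16 = 0 mg of change.

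**2. Table 4 followed for each starting dose, phosphate above 7 and up to 10 mg/dL and not settling.**

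| Step | 20 mg start | 16 mg start |
|---|---|---|
| First reduction | 20 to 16 mg | 16 to 12 mg |
| Still above 7 after 2 weeks | 16 to 12 mg (second reduction) | Further reduction required; it would fall below 12 mg, so the floor rule discontinues futibatinib |
| Still above 7 two weeks after the second reduction | Withhold, then resume at 12 mg | Not reached |

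The first step works for both. The paths part when both patients are at 12 mg with phosphate still above 7: one is withheld and resumed, the other is discontinued.

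**3. Phosphate above 10 mg/dL.** A 16 mg starter can have one interruption with reduction (to 12 mg). A second reduction meets the floor, so Table 4's trigger of two cannot be reached. The end point, discontinuation, is the same under either rule; the number of steps before it differs.

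**4. Chance that level -1 opens through the lead-in rule.** P(at least 2 DLTs in 6) = 1 − (1−p)^6 − 6p(1−p)^5. The documents give no true DLT rate, so p is assumed.

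- p = 10%: 1 − 0.5314 − 0.3543 = 0.114, or 11%.
- p = 20%: 1 − 0.2621 − 0.3932 = 0.345 (0.3446 unrounded), or 34%.

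The 30% rule in Section 7.3 adds to this by an amount not computed here.

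**5. Design figures.** P(declare promising) = sum over x = 3 to 12 of P(x responses in 12) × P(at least 7 − x responses in the next 12). This gives 4.87% at a 15% response rate and 86.2% at 40%, matching Section 7.1 and Table 11. Neither the starting dose nor the reduction ladder enters the formula.

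**The case against.** The best defence is that sites can work out what to do. The starting dose is clear where it is assigned (Section 4.1, Table 3), and the 20 mg sentence reads as general text that was not updated. The step size and floor define a path from 16 mg: down to 12 mg, then stop. Table 4 speaks of the next lower dose without naming one. Section 4.4 also lets treating physicians use their judgment, and level -1 may never open.

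Much of this stands, and it limits the point. A reader might infer each of the following, and the documents do not support them:

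- *That the reduction rules cannot be used at all from 16 mg.* The step from 16 to 12 mg can be followed.
- *That patients could be taken below 12 mg or left at 16 mg.* The floor rule excludes the first. The second needs an over-literal reading, since reductions are set at 4 mg.
- *That about 7 of 24 patients would be affected.* Section 2.4 reports phosphate above 7 mg/dL in 4 of 13 patients at 20 mg, and 24 × 4/13 = 7.4. That counts patients who enter the phosphate rule, not those still above 7 two weeks after reduction to 12 mg, for whom the documents give no rate. It also assumes the same rate at 16 mg.
- *That level -1 is more likely than not to open.* That needs a high DLT rate, such as 4/13 used as if it were one. The same 13 patients had no DLTs, and none were reported in the urothelial study, where 3 patients had completed cycle 1. Under Section 5.6, a value above 7 mg/dL alone does not establish a phosphate DLT.

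What the defence does not remove is the unequal outcome. Going to 12 mg and then stopping is exactly the path on which a 16 mg starter is discontinued where a 20 mg starter at the same dose and phosphate value is resumed. Nothing in the text shows that this difference was intended, and physician judgment does not reconcile the two rules.

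**Conclusion.** The point holds as a conflict between stated rules, confined to patients who start at 16 mg. For them Section 4.4 gives the wrong assigned dose, labels their starting dose as a reduction, and leaves one reduction where Table 4 relies on two. The second phosphate reduction, the withhold-and-resume step after it, and the trigger of two interruptions and reductions cannot be reached. The practical result is different handling at 12 mg with phosphate persisting above 7 and up to 10 mg/dL. Table 5's reduction by one dose level likewise has no defined level below -1.

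The size depends on level -1 opening: 11% to 34% under the lead-in rule for assumed true DLT rates of 10% to 20%, plus whatever the Section 7.3 rule adds. The number of patients who would need the second phosphate step cannot be estimated from the documents. A reader might infer that the error rates or the response analysis are compromised. They are not: type I error and power are unaffected, all treated patients are analysed for efficacy (Section 7.1), and an incorrect schedule excludes nobody (Section 7.2). Any effect on response would come through exposure and is not quantifiable here. The correction should be made before any patient starts at level -1.

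**What to change.** Reconcile Sections 4.1, 4.2 (Table 3), 4.4 (administration text, reduction text, Tables 4 and 5) and 7.1:

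- Refer the administered dose to the assigned dose level.
- Set out the permitted reductions separately for each starting level.
- State what Table 4's second-reduction steps, and its count of two interruptions and reductions, mean for a patient with one reduction available.
- Define what a reduction by one dose level means in Table 5 for a patient already at level -1.

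Which dose or discontinuation rule applies is for the sponsor and the investigator to decide; the review asks only that the passages agree. The cost is protocol wording and a small table, with no extra patients, procedures or change to the statistical design.
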